
	1. change in Everyday Cognition (score range: 1 to 4)		
	2. change in Geriatric Depression Scale score (score range: 0 to		
	15)		
	3. change in Pittsburgh Sleep Quality Index global score (score		
	range: 0 to 21)		
	4. change in EuroQol EQ-D5 utility score (score range: -1 to 1)		
Covariates	There are no pre-specified covariates for the primary and secondary		
	endpoints.		
Follow-up schedule	16 weeks (mid point), 24 weeks (intervention termination), 48 weeks		
,	(post-intervention follow-up)		
Masking	Outcome assessors, data analysts		
Number of subjects	The target sample size is 315 participants to provide 80% power to		
3	detect a medium-size difference in mean MoCA change of 1.5 points		
	between the cognitively enhanced tai ji quan and the standard tai ji		
	quan groups and a large-size difference of 3 points between the		
	cognitively enhanced tai ji quan and the stretching control groups at 24		
	weeks.		
Statistical analysis	The effect of the intervention on the primary endpoints will be		
	evaluated using the intention-to-treat approach, in which participants		
	are grouped according to randomization assignment. To compare		
	change in outcome measures among the three intervention groups at 6		
	months, we will analyze a 3 (Group) by 3 (Time) mixed-effects model		
	with repeated measures on the second factor (i.e., outcome measures		
	assessed at baseline, 4 months, and 6 months). In the presence of a		
	Group by Time interaction effect, pre-specified follow-up pair-wise		
	comparisons will be performed to determine between-group		
	differences (indicated below). Secondary outcomes will be similarly		
	analyzed. Results from primary analyses will be presented as the		
	difference in mean MoCA and dual-task performance between the		
	cognitively enhanced tai ji quan and standard tai ji quan groups and		
	between the cognitively enhanced tai ji quan and the stretching		
	exercise control, with a Bonferroni-adjusted 2-tailed significance level		
	of .0125 for each of the two primary outcomes and a 98.75%		
Intonia analysis	confidence interval.		
Interim analysis	No interim analyses for efficacy or futility. However, interim		
	monitoring is performed with a focus on subject accrual, intervention		
	fidelity, protocol adherence, data completeness and quality, and		
	intervention safety and analysis.		

Study Background and Rationale

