Secondary hypothesis: We hypothesize that compared with standard tai ji quan or stretching control, participants in the cognitively enhanced tai ji quan training will retain their intervention gains in the primary outcomes of global cognition and dual-task gait performance at 12 months (post-intervention) follow-up. We also hypothesize that cognitively enhanced tai ji quan training will continue to be superior to either standard tai ji quan or stretching control, at 12-month follow-up, in terms of sustaining the training effect on slowing disease progression to dementia, as indexed by the continued improvement in the mean CDR-SB score from baseline.

Study design

This study is designed as a prospective, assessor-blinded, 3-arm parallel group, randomized clinical trial with a 1:1:1 allocation ratio. The primary co-outcome measures are global cognition function and dual-task walking costs. The target sample size is 315 participants, enrolled from local communities. The goal is to detect, with 80% power, 1.5 points in MoCA between the cognitively enhanced tai ji quan and the standard tai ji quan groups and 3 points between the cognitively enhanced tai ji quan and the stretching control groups at 24 weeks. The study will consist of a 6-month acute intervention phase (designed for addressing the primary aim) followed a 6-month maintenance phase (for addressing the secondary aim).

Outcomes

Table 1 below describes the study's primary, secondary, and tertiary outcomes, source of data, and follow-up schedule.

	Measure	Data source	Follow-up schedule
Primary outcome			
Global cognition	Montreal Cognitive Function	Assessment	4 months, 6 months,
-	measure	conducted by	and 12 months
	(MoCA; score range: 0 to 30)	assessors	
Dual-task walking costs	Difference between single-	Assessment	4 months, 6 months,
	and dual-task gait speed	conducted by	and 12 months
	(expressed in percentage)	assessors	
Secondary outcome			

Cognition and function	Clinical Dementia Rating Sum of Boxes score (range: 0 to 18)	Interviews with participants and informants conducted by assessors	4 months, 6 months, and 12 months
Executive function	Trail Making Test (B) (measured in seconds)	Cognitive assessment conducted by assessors	4 months, 6 months, and 12 months
Attention and memory	Category Fluency (number of animal names recalled)	Cognitive assessment conducted by assessors	4 months, 6 months, and 12 months

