In the presence of a Group by Time interaction effect, follow-up pair-wise comparisons, using independent t tests, will be performed to identify a priori specified between-group differences. Specifically, we will determine the intervention effect of cognitively enhanced tai ji quan for change in MoCA and costs of dual task in gait performance from baseline to 24 weeks by making a comparison between cognitively enhanced tai ji quan and standard tai ji quan and between cognitively enhanced tai ji quan and stretching exercise.

Level of statistical significance and confidence intervals. Our primary outcome analyses will be 2-sided with an adjusted significance level of <0.0125 (0.05 / 4 comparisons) and a 98.75% confidence interval (CI). For each group, both estimated means and their corresponding standard error of estimates at each assessment point will be presented. In presenting between-group differences, mean differences with CIs will be presented. SPSS "MIXED" function will be used in analyzing our primary outcomes.

Secondary and tertiary outcome analyses

A similar analytic approach will also be applied to all secondary and tertiary (continuous) outcome variables described in Table 1. All study outcomes are expected to follow a normal distribution. In the case of deviation from normality, generalized estimating equations will be used to assess the effect of intervention over time. No Bonferroni correction will be made to account for multiple comparisons.

Level of statistical significance and confidence intervals. All tests and CIs will be 2-sided, and statistical significance will be defined as a P value of <0.05. For each group, we will report both estimated means and their corresponding standard error of estimates at each assessment point. In presenting between-group differences at 24 weeks, estimated mean differences with CIs will be presented.

Analyses on examining intervention durability at 48-week follow-up

We will use the same analytic strategy outlined in our primary and secondary outcome analyses, with the exception of CDR-SB (described in detail below), to examine whether the intervention effects will persist 24 weeks after the end of the 24-week supervised interventions (*Secondary hypothesis*).

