Note: Group is a binary variable involving a comparison between cognitively enhanced tai ji quan and standard tai ji quan or cognitively enhanced tai ji quan and stretching exercise.

Post-hoc exploratory analyses

No pre-specified post-hoc exploratory analyses are planned.

Subgroup analyses

In light of the findings reported in prior studies, 36,37 we also plan to conduct a series of subgroup analyses. Specifically, using a three-way interaction model that involves factors of Group, Time, and Subgroup, we will examine whether the expected between-group differences in the two primary outcomes are associated with pre-specified subgroups that include sex (1 = men, 2 = women), age (1 = 65-74, 2 = 75-84, 3 = 85+ years old), and level of education (1 = high school diploma or lower, 2 = college degree or higher). We are aware of the fact that these subgroup analyses are not powered statistically, and we will therefore interpret any statistically significant results with caution. All subgroup analyses are based on an alpha level of <0.05.

Power estimation for primary outcomes

This study is powered to detect a mean difference in change in the primary outcomes of MoCA and motor-cognitive dual-task gait performance between (a) the cognitively enhanced tai ji quan intervention and a standard tai ji quan intervention operationalized by TJQMBB, ¹⁰ and (b) the cognitively enhanced tai ji quan intervention and a non-tai ji quan control condition – stretching – at 6 months, among older adults with MCI. We estimated the magnitude of the effect size (difference score divided by its pooled standard deviation) that is detectable with at least 80% power using a 2-sided 0.05-level test. We expect that participants in the cognitively enhanced tai ji quan intervention would experience a clinically meaningful improvement of at least 1 score unit in MoCA and a 10% reduction in dual-task costs on gait performance speed between the enhanced tai ji quan intervention and each of the two comparison arms. The following details the parameters used and results of our power analyses for each of the two primary outcomes.

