Efficacy analyses. The effect of intervention on the co-primary study outcomes will be evaluated using an intention-to-treat approach in which participants will be analyzed according to randomization assignment. A modified intention-to-treat analysis will be conducted that includes all participants who have undergone randomization and have completed all study follow-up assessments, regardless of their participation adherence status. Finally, a per-protocol analysis will include participants in the intention-to-treat population who have an overall class attendance rate of $\geq 75\%$ (out of the total planned 48 intervention class sessions) of their assigned exercise intervention.¹⁰

Co-primary endpoint analyses

To test the *Primary hypothesis*, we plan to use a generalized linear mixed model with random intercepts and fixed treatment effects for the primary outcomes. Specifically, we will determine the intervention effect through an analysis of a 3 (Group) by 3 (Time) mixed-effects model with repeated measures (follow-up time point) on the second factor (i.e., outcome measures assessed at baseline, 4 months [mid-point], and 6 months [intervention termination]).

In the presence of a Group by Time interaction effect, follow-up pair-wise comparisons, using independent t tests, will be performed to identify a priori specified between-group differences. Specifically, we will determine the intervention effect of cognitively enhanced tai ji quan for change in MoCA and costs of dual task in gait performance from baseline to 24 weeks by making a comparison between cognitively enhanced tai ji quan and standard tai ji quan and between cognitively enhanced tai ji quan and stretching exercise.

Level of statistical significance and confidence intervals. Our primary outcome analyses will be 2-sided with an adjusted significance level of <0.0125 ($0.05 / 4$ comparisons) and a 98.75% confidence interval (CI). For each group, both estimated means and their corresponding standard error of estimates at each assessment point will be presented. In presenting between-group differences, mean differences with CIs will be presented. SPSS “MIXED” function will be used in analyzing our primary outcomes.

Secondary and tertiary outcome analyses

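### The 80% power for the 1.5-point MoCA contrast is computed at two-sided 0.05, but the contrast is tested at 0.0125, where power is about 63% if the SD of 3.5 is the SD of change

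*Protocol*

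**What the plan says.** The section on power estimation for primary outcomes appears both in the protocol's SAP chapter and in the stand-alone SAP. It looks for the effect "detectable with at least 80% power using a 2-sided 0.05-level test" and defines "effect size (difference score divided by its pooled standard deviation)". For MoCA it assumes two repeated measurements, a correlation of 0.7 and 267 participants. It claims more than 80% power for a difference in mean change of 1.5 points (SD 3.5, d = 0.4) between enhanced and standard tai ji quan, and for 3 points (SD 3.5, d = 0.8) against stretching. A 15% loss brings enrolment to 315.

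The section on co-primary endpoint analyses tests at a different level. It calls for "follow-up pair-wise comparisons, using independent t tests", at an "adjusted significance level of <0.0125 (0.05 / 4 comparisons) and a 98.75% confidence interval". The stand-alone SAP repeats the "adjusted significance level of <0.0125".

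The 80% figure also appears without an alpha beside it. The synopsis says "The target sample size is 315 participants to provide 80% power to" detect these differences, and its statistical analysis entry gives .0125 as the test level. The study design section says "The goal is to detect, with 80% power, 1.5 points in MoCA" for the first contrast.

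**The concern.** Power belongs to a particular test at a particular level. Here the level in the calculation is four times the level in the analysis, so the 80% does not describe the test that will decide the primary hypothesis. A reader of the synopsis alone sees 80% power and a .0125 test and will put the two together.

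The contrast exposed to this is enhanced versus standard tai ji quan, the one that isolates the added cognitive component. A non-significant result there could be read as a miss by an 80%-powered test when the power may have been well below that. Type I error control is not in question.

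**Working it through.** **Inputs.** From the power section: differences of 1.5 and 3 points, SD 3.5, d = 0.4 and 0.8, correlation r = 0.7, 267 evaluable, 15% loss, alpha 0.05. From the study design section: 1:1:1 allocation, so 267/3 = 89 per arm. From the co-primary analysis section: independent t tests at two-sided 0.05/4 = 0.0125.

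**Enrolment.** 267/(1 − 0.15) = 314.1, so 315 is reproduced.

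**Formula.** Power is the probability that a noncentral t variable with 2n − 2 degrees of freedom and noncentrality δ = d·√(n/2) exceeds the two-sided critical value in absolute size.

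**Reading A: 3.5 is the SD of change.** d = 1.5/3.5 = 0.4286 and δ = 0.4286 × √(89/2) = 2.859.
- At 0.05 the critical value is 1.974 and power is 81.1%. This reproduces the claim of more than 80%.
- At 0.0125 the critical value is 2.524 and power is 63.2%.

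**Reading B: 3.5 is a single-visit SD and r = 0.7 enters through the change score.** SD of change = 3.5 × √(2 × (1 − 0.7)) = 2.71, so the effect size is divided by √0.6 = 0.775. The stated d = 0.4 becomes 0.516, and 0.4286 becomes 0.553.

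| 1.5-point contrast, 89 per arm | Power at 0.05 | Power at 0.0125 | Per arm for 80% at 0.05 | Per arm for 80% at 0.0125 |
|---|---|---|---|---|
| A, d = 0.4286 | 81.1% | 63.2% | 87 | 123 |
| A, d = 0.4 as stated | 75.6% | 55.8% | 100 | 141 |
| B, d = 0.4 as stated | 92.9% | 82.0% | 60 | 86 |
| B, d = 0.4286 | 95.6% | 87.7% | 53 | 75 |

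**More data than planned for.** Table 2 of the data completeness section projects 90% of primary data at 6 months: 315 × 0.90/3 = 94.5, taken as 94 per arm. Under reading A at 0.0125 that gives 66.1%. With all 315 contributing (105 per arm) it gives 72.0%.

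**Detectable difference and break-even.** With 89 per arm, 80% power at 0.0125 requires d = 0.505. Under A that is 0.505 × 3.5 = 1.77 points (1.48 at 0.05); under B it is 0.505 × 2.71 = 1.37 points. For 1.5 points, the SD of change would have to be at most 1.5/0.505 = 2.97. With a single-visit SD of 3.5, this means r of at least 1 − 2.97²/(2 × 3.5²) = 0.64.

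**The 3-point contrast.** At 0.0125 with 89 per arm, power is 99.7% with d = 0.8 and 99.9% with d = 3/3.5 = 0.857 under A, and higher still under B.

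**Dual-task cost.** The power section says that this co-primary outcome is powered too and gives targets of 10% and 20%, but no SD. Its power cannot be calculated at either alpha.

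**The case against.** The best counter-argument is that reading A sets aside two of the plan's own inputs. It makes no use of the correlation of 0.7, and it replaces the stated d = 0.4 with 0.4286; with d = 0.4 it gives 75.6% at 0.05 and misses the claimed figure. Reading B uses d = 0.4 and r = 0.7, gives 82.0% at 0.0125, and needs 86 per arm (258 in total), not far from 267. The sponsor may have calculated at 0.0125 and written 0.05 by mistake. If r = 0.7 enters through baseline adjustment instead, the SD is 3.5 × √(1 − 0.49) = 2.50 and power at 0.0125 is about 93%.

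This stands as a reason to treat 63% as conditional. It does not rescue the text. At the level that the plan states, reading B gives 93% to 96% and would need only 53 to 60 per arm for 80%, so it does not explain 267. It works only if the stated 0.05 is wrong. Reading A also fits the wording better: the effect size is a difference score over its own pooled SD, the 3.5 is attached to mean change, and the tests named are independent t tests.

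It is also fair to say that the planned mixed model with multiple imputation is richer than a two-group t test on 89 per arm. The 66% and 72% figures give some measure of what more data would add, and both remain below 80%. Against that, the pairwise tests are run only after a Group by Time interaction, a condition that cannot raise power; its effect was not quantified. Finally, the 0.05 is openly stated in the power section and the 98.75% intervals will show the precision achieved. Both points limit the harm without making the synopsis correct.

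**Conclusion.** The concern holds. That the stated 80% is tied to 0.05 while the primary tests run at 0.0125 is plain from the text and needs no assumption. The size of the gap does need one. If 3.5 is the SD of change, which is the better-supported reading, power for the 1.5-point contrast is about 63% with 89 per arm, and confidence in that figure is moderate. If 3.5 is a single-visit SD with r = 0.7 applied to the change, there is no shortfall, but the stated alpha is wrong and the effect-size definition does not fit. The power section needs correction on either reading. The contrast with stretching is safe throughout. This should be fixed because a headline figure is misdescribed; the error rate and the validity of the analysis are unaffected. The missing dual-task SD is a lesser gap of detail.

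**What to change.** 1. In the power section, state whether 3.5 is the SD of change or of a single visit, how the 0.7 entered, which effect sizes were used (0.4 and 0.8, or 0.43 and 0.86), and the alpha.
2. Restate power at two-sided 0.0125 in the synopsis, the study design section and the power section, in both documents where they repeat. If 3.5 is the SD of change, give about 63% for 1.5 points with 89 per arm, or 80% for about 1.77 points. If the single-visit reading was used, give its formula and its power at 0.0125, and correct the effect-size definition and the 0.05.
3. Give the SD behind the dual-task targets, or withdraw the claim that this outcome is powered.

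Leave the 0.0125 rule, the 98.75% intervals, the analysis and the sample size as they are. The cost is retrieving the original power inputs and rewording these sections. No participants are added. Under the SD-of-change reading, the trial will have to state a less favourable power.

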 $\underline{\text{MoCA}}$. Assuming two (pre and post) repeated measurements and a between-level correlation of 0.7, the planned sample size of 267 participants would provide >80% power to detect a medium-size difference (Cohen d = 0.4) in mean MoCA change of 1.5 points (SD = 3.5) between the cognitively enhanced tai ji quan and the standard tai ji quan groups and a large-size difference (Cohen d = 0.8) of 3 points (SD = 3.5) between the cognitively enhanced tai ji quan and the stretching control groups at 6 months. No minimal clinically important difference (MCID) in MoCA has been established in the physical exercise literature, but our target estimate is close to that of 1.22 points established for the stroke patient population.³⁸

Dual-task gait performance. Using the same assumptions, at 6 months, we estimated a 10% reduction in dual-task walking costs between the cognitively enhanced tai ji quan and standard tai ji quan interventions and a 20% reduction between cognitively enhanced tai ji quan and stretching interventions. At the time of developing this research proposal, no MCID for reduction in costs in dual-task performance in gait is available. The target estimates calculated in this trial were inferred from our prior completed studies. ^{10,12}

Taking into account a conservative 15% loss during the 6-month active intervention period, a total of 315 participants was planned for the study.

Treatment of noncompliance and missing data

All enrolled study participants will be followed until the trial period ends, whether or not the participant is still receiving or complying with the intervention. Primary endpoint analyses will be conducted according to the original randomization scheme in an intention-to-treat approach. We will use a multiple imputation data method for missing data. We plan to perform 10 sets of imputations. Variables without missing data to be used for prediction of imputed values on the study variables will include baseline measures of age, sex, level of education, MMSE, number of chronic conditions, and depression. The imputed data will be submitted to the same analytic model (i.e., linear mixed model) as the non-imputed observed data, and the results of each analytic model will be pooled across the 10 imputed data

sets. The secondary outcome analyses will also be conducted using the multiple imputation method described above. Tertiary outcome analysis will be conducted with observed data without imputation.

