Intervention fidelity will focus primarily on issues such as (a) interventionist qualifications and training, (b) teaching quality of the individual forms/movements or routine in each session, (c) exercise intensity and consistency in training dosage across different sites, and (d) weekly class attendance checking and monitoring. The evaluation will be conducted monthly by either an authorized research team member or an instructor, per guidelines specified in an established fidelity checklist. ¹⁰ In evaluating the item in (b), high intervention fidelity will be considered achieved if at least 95% of the mandatory components (overall completion of pre-specified activities, quality of verbal and visual instructions, emphasis of core training points, session completion time) are fully or partially delivered in each session. Deviations related to intervention delivery protocol will be captured on a protocol deviation form and be entered into a project database for evaluation by the research staff and Principal Investigator. Prompt action will be taken by the Principal Investigator to remedy any problems and deviations identified.

Data completeness and quality control

Data completion refers to the study measurement ascertainment status from all enrolled study participants. The project strives to collect study outcome measures on every participant at each scheduled time point (baseline, 4 months, 6 months, and 12 months), regardless of his/her intervention participation status. As specified in the protocol for the study, we have planned an overall study retention rate of 85% (i.e., having primary and secondary outcome measures available on 85% of the enrolled participants and their informants). To accomplish this goal, planned measures will be taken to ensure that as many participants as possible, including dropouts, attend each scheduled in-person assessment visit at our research facilities. Our proactive methods will include frequent telephone and e-mail contacts with subjects who miss scheduled data assessment appointments. The planned completion of data ascertainment at each follow-up time point is described in the Table 2 below.

Table 2. Projected completion of data ascertainment on study outcome measures at each measurement time point

Measure\Time point	4 months	6 months	12 months
Primary	95%	90%	85%
Secondary	95%	90%	85%
Tertiary	95%	90%	85%

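### With 10 imputations, a primary p-value near 0.0125 depends on the random seed; 100 imputations and a recorded seed would largely remove this at trivial cost

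*Protocol*

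**What the plan says.** The text is the same in the SAP section of the protocol and in the separate SAP document.

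- **Treatment of noncompliance and missing data.** The primary analysis is intention-to-treat with multiple imputation: "We plan to perform 10 sets of imputations". The linear mixed model is fitted to each set, and "the results of each analytic model will be pooled across the 10 imputed data" sets. The predictors named for imputation are "baseline measures of age, sex, level of education, MMSE, number of chronic conditions, and depression".
- **Co-primary endpoint analyses.** Primary tests are "2-sided with an adjusted significance level of <0.0125 (0.05 / 4 comparisons"), with 98.75% confidence intervals.
- **Missing data expected.** Table 2 (Data completeness and quality control) projects 90% completeness of the primary outcomes at 6 months. The sample size allows for more loss: "Taking into account a conservative 15% loss during the 6-month active intervention period, a total of 315 participants was planned for the study".

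Neither document gives a random seed, a reason for choosing 10, or a check of Monte Carlo error.

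**The concern.** A pooled multiple-imputation result has two sources of variation: the sampling of participants, and the random draws used to fill in missing values. The second shrinks as imputations are added. Ten sets are ample for efficiency, but the pooled test statistic still moves by roughly a tenth of a standard error from seed to seed. That is harmless when the p-value is far from the threshold. When it is close, an independent analyst who re-runs the same data with another seed may cross 0.0125 and report a different conclusion. Such re-runs are foreseeable, since the Programming plan offers programs and data on request.

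**Working it through.** **1. The plan's own figures.** 0.05/4 = 0.0125, so the two-sided critical z is 2.498. 267/(1 − 0.15) = 314.1, rounded up to 315, or 105 per arm (89 evaluable per arm from 267). Power for 1.5 points with SD 3.5 and 89 per arm is 0.816 at the 0.05 level used in the power section, which meets the stated >80%. All three reproduce.

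**2. The assumed input.** The fraction of missing information (FMI) is not in the documents. I take 0.10 as the central value, with a range of 0.03 to 0.20.

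**3. Efficiency.** Relative efficiency = 1/(1 + FMI/m) = 1/(1 + 0.10/10) = 0.990.

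**4. Seed-to-seed noise.** The SD of the pooled z over seeds is about √(FMI/m). For FMI 0.10 and m = 10 this is √0.01 = 0.100. The 95% seed range around the threshold is 2.498 ± 1.96 × 0.100 = 2.302 to 2.694, which is p = 0.0214 to 0.0071. For m = 100 the SD is 0.032.

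| FMI | 95% seed range of p, m = 10 | 95% seed range of p, m = 100 |
|---|---|---|
| 0.03 | 0.0092–0.0168 | 0.0114–0.0137 |
| 0.10 | 0.0071–0.0214 | 0.0105–0.0149 |
| 0.20 | 0.0055–0.0264 | 0.0097–0.0160 |

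**5. Simulation check.** Two arms of 105, SD 3.5 at each visit, correlation 0.7, change-score comparison, Rubin's rules with small-sample degrees of freedom. There were 15 data sets per scenario, each shifted so that p = 0.0125 with unlimited imputations.

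| Imputation model | Missing | FMI | m = 10 | m = 100 |
|---|---|---|---|---|
| Group, baseline outcome | 10% | 0.08 | 0.0072–0.0228 | 0.0105–0.0151 |
| Group, baseline and 4-month outcome | 10% | 0.07 | 0.0076–0.0216 | 0.0107–0.0145 |
| Group only | 10% | 0.13 | 0.0059–0.0285 | 0.0099–0.0158 |
| Group, baseline outcome | 15% | 0.14 | 0.0060–0.0292 | 0.0101–0.0157 |
| Group, baseline and 4-month outcome | 15% | 0.12 | 0.0064–0.0269 | 0.0103–0.0153 |
| Group only | 15% | 0.19 | 0.0049–0.0357 | 0.0094–0.0169 |

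The simulation agrees with the formula, with a slightly longer upper tail at m = 10.

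**6. How often the seed would change the verdict.** Let Z be the statistic with unlimited imputations, Z ~ N(μ, 1), and let each seed add N(0, s²) with s = √(FMI/m). Two seeds disagree with probability E[2π(1 − π)], where π = Φ((Z − 2.498)/s). At FMI 0.10:

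- *Enhanced versus standard, 1.5 points, 3.5 as the SD of change.* μ = 1.5/(3.5 × √(2/89)) = 2.86. Disagreement is 4.2% with m = 10 and 1.3% with m = 100. At FMI 0.03 these are 2.3% and 0.7%; at 0.20, 5.9% and 1.9%.
- *The same contrast, 3.5 as the per-visit SD with correlation 0.7.* SD of change = 3.5 × √(2 × 0.3) = 2.71 and μ = 3.69. Disagreement is 2.2% and 0.7%.
- *Enhanced versus stretching, 3 points.* μ = 5.72. Disagreement is about 0.03% with m = 10.
- *Dual-task cost.* The power section gives no SD, so μ cannot be computed.

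**The case against.** Several objections have force.

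**The inference is sound.** Rubin's rules remain valid at m = 10, efficiency is about 99%, and the type I error is not inflated. A reader might infer that 10 imputations make the primary tests invalid or biased. Nothing in the documents or the calculations supports that; only reproducibility near the threshold is affected.

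**The risk is easily overstated.** About 15% of trials at μ = 2.86 would have a statistic within 1.96 seed-SDs of the threshold. A reader might take that as the chance that the seed decides the result. It is not, because many of those trials have only a few percent chance of crossing. The chance that two seeds disagree is about 4%, and about 2% on the per-visit reading of the SD, which the power section leaves open.

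**Only one contrast is clearly exposed.** A reader might extend the figure to all four primary comparisons. The 3-point MoCA contrast is far from the threshold, and the two dual-task contrasts cannot be assessed.

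**The plan has seed-free comparisons.** It refers to the same model on observed data and plans a completers-only modified intention-to-treat analysis. A recorded seed would also make a re-run identical at m = 10. These help, but they do not stop the primary result itself from depending on an arbitrary seed. Fixing the seed makes the number repeatable without making it less arbitrary.

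**Timing.** The title pages cite publication of the main results in October 2023, while this version is dated September 2024. Changing the number of imputations after results are known would be post hoc. This stands, and it governs how the fix should be presented.

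**Conclusion.** The point holds as a minor, near-costless gain in precision. At an assumed FMI of 0.10, moving from 10 to 100 imputations narrows the 95% seed range of a borderline p-value from about 0.007–0.021 to about 0.0105–0.015. For the enhanced versus standard MoCA contrast at the planned effect, it cuts disagreement between two seeds from about 4% to about 1% of trials (about 2% to 0.7% if 3.5 is the per-visit SD).

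This rests on the FMI, which the documents do not supply, and on treating the contrast as a simple comparison of change between two arms. An FMI of 0.03 roughly halves the noise. The 15% loss allowed for in the sample size, or an imputation model limited to weak predictors, would increase it. The direction does not change anywhere in the range examined. If the observed p-values lie well away from 0.0125, the choice of 10 has no practical consequence.

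**What to change.** In Treatment of noncompliance and missing data, change 10 imputations to 100, state a fixed seed to be recorded with the analysis program, and report the Monte Carlo error of each primary estimate alongside its p-value and confidence interval. The seed range shrinks by a factor of √10 but does not vanish, so the Monte Carlo error is still needed when a result is close to 0.0125.

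If the primary results are already known, leave the pre-specified 10-imputation analysis as it is and present the 100-imputation run as a labelled confirmatory re-run.

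The cost is minutes of computing for a linear mixed model in 315 participants, plus a sentence or two in the plan.
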